- Evidence of latent or active tuberculosis (TB), excluding patients receiving chemoprophylaxis for latent TB infection

A TB test (tuberculin skin test and/or an interferon-gamma release assay [e.g., QuantiFERON®-TB Gold In-Tube assay, T-SPOT TB assay]) should be conducted according to local guidance. If a patient is positive for latent TB, then the patient must be treated with appropriate anti-mycobacterial therapy for at least 4 weeks prior to initiating study treatment administration. Refer to Appendix 5 for details on TB screening and treatment.

- Receipt of live or live attenuated vaccine within 6 weeks prior to baseline
- History of blood donation (one unit or more), plasma donation or platelet donation within 90 days prior to screening and Day 1
- History of malignancy within the last 5 years, including solid tumors, hematologic malignancies and in situ carcinoma (except basal cell and squamous cell carcinomas of the skin, or in situ carcinoma of the cervix uteri that have been completely excised and cured)
- History of severe allergic reaction to a biologic agent (e.g., shock, anaphylactic reactions)
- Active suicidal ideation within 6 months prior to screening or history of suicide attempt within 3 years prior to screening
- Any serious medical condition or abnormality in clinical laboratory tests that, in the investigator's judgment, precludes the patient's safe participation in and completion of the study

 Pregnant or breastfeeding, or intending to become pregnant during the study or within 3 months after the final dose of satralizumab

Female patients of childbearing potential must have a negative serum pregnancy test result at screening prior to initiation of study drug.

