# Columbia-Suicide Severity Rating Scale (C-SSRS)

The C-SSRS is a tool used to assess the lifetime suicidality of a patient and to track suicidal events throughout treatment. The scale will be administered at the time points indicated in the schedule of activities (see Appendix 1 and Appendix 2) for prompt recollection of suicidal ideation, including the intensity of the ideation, behavior and attempts with actual and potential lethality. The "C-SSRS at baseline" will be collected at baseline, and the "C-SSRS since last visit" will be collected at subsequent visits.

Examples of the C-SSRS forms are included in Appendix 11 and Appendix 12.

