5. Active Suicidal Ideation with Specific Plan and Intent Thoughts of killing oneself with details of plan fully or partially worked Have you started to work out or worked out the details of how to kill y	d out and subject has some intent to carry it out.	Yes	No
If yes, describe:			
INTENSITY OF IDEATION			
The following features should be rated with respect to the most and 5 being the most severe). Ask about time he/she was feeling	severe type of ideation (i.e., 1-5 from above, with 1 being the least severe the most suicidal.		ost
Most Severe Ideation:			vere
Type # (1-5)	Description of Ideation		
Frequency  How many times have you had these thoughts?  (1) Less than once a week (2) Once a week (3) 2-5 times in we	sek (4) Daily or almost daily (5) Many times each day	-	_
Duration When you have the thoughts, how long do they last?			
(1) Fleeting - few seconds or minutes (2) Less than I hour/some of the time (3) 1-4 hours/a lot of time	(4) 4-8 hours/most of day (3) More than 8 hours/persistent or continuous	-	_
Controllability	ing to English and the		
Could/can you stop thinking about killing yourself or want (1) Easily able to control thoughts	(4) Can control thoughts with a lot of difficulty	_	
(2) Can control thoughts with little difficulty     (3) Can control thoughts with some difficulty	(5) Unable to control thoughts (0) Does not attempt to control thoughts		
Deterrents			
thoughts of committing suicide?	n, pain of death) - that stopped you from wanting to die or acting on		
(1) Deterrents definitely stopped you from attempting suicide (2) Deterrents probably stopped you (3) Uncertain that deterrents stopped you	(4) Determents most likely did not stop you (5) Determents definitely did not stop you (0) Does not apply	-	
	ing to die or killing yourself? Was it to end the pain or stop the way with this pain or how you were feeling) or was it to get attention,		
(1) Completely to get attention, revenge or a reaction from others (2) Mostly to get attention, revenge or a reaction from others (3) Equally to get attention, revenge or a reaction from others and to end/stop the pain.	(4) Mostly to end or stop the pain (you couldn't go on living with the pain or how you were feeling) (3) Completely to end or stop the pain (you couldn't go on living with the pain or how you were feeling) (0) Does not apply	-	_
-		Versi	on 1/14/09

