4.5.5 ECGs

ECG data will be summarized by treatment group for each assessment visit using descriptive statistics of absolute values and change from baseline values for the following parameters:

- Heart rate
- QRS duration
- RR interval
- PR interval
- QT interval

In addition, ECG overall interpretations will be summarized by treatment group and visit.

4.5.6 Columbia Suicide Severity Rating Scale (C-SSRS)

The Columbia Suicide Severity Scale (C-SSRS) is an assessment tool used to assess the lifetime suicidality of a participant (C-SSRS at baseline) as well as any new instances of suicidality (C-SSRS since last visit). The structured interview prompts recollection of suicidal ideation, including the intensity of the ideation, behavior, and attempts with actual or potential lethality.

- Suicidal ideation, suicidal behavior, and self-injurious behavior without suicidal intent
 will be summarized by treatment group at each assessment visit. In addition,
 change from baseline to worst post-baseline assessment in suicidality.
- Categories will be summarized by treatment group.

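### The suicidality change summary compares a lifetime C-SSRS baseline with a since-last-visit rating, so new suicidality at or below the lifetime worst reads as unchanged or improved

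*SAP*

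**What the plan says.** SAP 4.5.6 describes the C-SSRS as "used to assess the lifetime suicidality of a participant (C-SSRS at baseline) as well as any new instances of suicidality (C-SSRS since last visit". Protocol 4.5.8.2 agrees: the scale is "used to assess the lifetime suicidality of a patient and to track suicidal events throughout treatment", with one form at baseline and a different form afterwards.

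SAP 4.5.6 then plans two outputs:

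- Ideation, behavior and self-injury without suicidal intent, which "will be summarized by treatment group at each assessment visit".
- A "change from baseline to worst post-baseline assessment in suicidality". This sentence has no verb, and the next bullet opens "Categories will be summarized by treatment group". Read together, they describe a change in suicidality categories, tabulated by arm.

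Change from baseline in suicidality is a listed safety endpoint (protocol Table 2, SAP Table 1). Protocol 4.1.2.3 excludes patients with "Active suicidal ideation within 6 months prior to screening or history of suicide attempt within 3 years prior to screening", so older history is admitted.

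**The concern.** A change from baseline means something only if both ratings describe comparable periods. Here the first covers a whole life and the second a few weeks. The eligibility rule sharpens the mismatch: recent active ideation and recent attempts are excluded, so a positive baseline entry for either should mostly reflect old history, not the patient's state at first dose.

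A participant with type 4 ideation many years ago and new type 3 ideation on treatment would appear in the change summary as better. A reader who relies on that summary for a stated safety endpoint could miss new on-treatment ideation, and could see apparent improvement in both arms that reflects only the recall period.

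**Working it through.** The plan states no figure for this analysis, so there is none to reproduce. The check compares the recall periods and then enumerates the possible shifts.

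**Recall periods**

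1. Baseline form (protocol Appendix 11): ideation is rated at the lifetime worst point, and the intensity section tells the rater "Ask about time he/she was feeling" most suicidal. Behavior is recorded under a lifetime heading. As reproduced, the form has no recent window.
2. Follow-up form (protocol Appendix 12): ideation and behavior are both recorded under a since-last-visit heading.
3. Schedule (protocol Appendix 1): the C-SSRS is first given at Week 0 and not at screening. In the double-blind period the lifetime rating is therefore the only pre-dose rating.
4. Baseline rule (SAP 4.1): baseline is the last value before first dose unless stated otherwise. SAP 4.5.6 states no exception.

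**Shift grid**

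Let h be the lifetime-worst ideation type at baseline and w the worst on-study type (0 = none). A shift reads as worse (W) if w > h, unchanged (=) if w = h, and improved (I) if w < h.

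| h | w=1 | w=2 | w=3 | w=4 | w=5 |
|---|---|---|---|---|---|
| 0 | W | W | W | W | W |
| 1 | = | W | W | W | W |
| 2 | I | = | W | W | W |
| 3 | I | I | = | W | W |
| 4 | I | I | I | = | W |
| 5 | I | I | I | I | = |

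For participants with past ideation (h = 1-5) and new on-study ideation (w = 1-5):

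- Worse: 4+3+2+1+0 = 10 of 25.
- Unchanged: 5 of 25.
- Improved: 0+1+2+3+4 = 10 of 25.

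So 15 of 25 cells read as no worsening. At h = 5 no on-study ideation can read as worse. With w = 0, every row from h = 1 to h = 5 reads as improved although nothing happened on study. A count of on-study incidence would record all 25. These are counts of cells, not expected frequencies of participants.

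**Illustrative counts of participants**

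The documents give no rates, so everything here except the arm size is assumed: lifetime active ideation in 5-15%; 24-week ideation in 10-20% of those with such a history; types 2-5 equally likely, so that 10 of 16 cells (0.625) have w at or below h. Arm size is 185/2, about 92.

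- New ideation read as no worsening, per arm: 92 × history × risk × 0.625. Low: 92 × 0.05 × 0.10 × 0.625 = 0.3. High: 92 × 0.15 × 0.20 × 0.625 = 1.7.
- Old history with no event, read as improved, per arm: 92 × history × (1 − risk). Low: 92 × 0.05 × 0.80 = 3.7. High: 92 × 0.15 × 0.90 = 12.4.

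**The case against.** The strongest reply is that a change in categories is naturally shown as a shift table. A full table of lifetime category by worst on-study category puts each participant in a visible cell, and its margins give the worst on-study category by arm. The SAP never uses the label improved. The by-visit summaries need no baseline, adverse events are tabulated per participant (SAP 4.5.2), and the iDMC reviews unblinded safety data about every 3 months.

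Much of this stands. A reader might infer that events are lost; they are not, because the by-visit summaries show them. A reader might infer that one numeric score is subtracted from another; the SAP defines no score, and the two bullets read as a category shift. A reader might infer that any past history masks new ideation; 10 of the 25 cells still read as worse. A past attempt followed by new ideation cannot be classed at all, since the SAP does not rank behavior against ideation.

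Two things do not fall away. First, the SAP does not commit to a full cross-tabulation; it specifies a change from a lifetime rating, and the direction of that change is misleading in whatever table carries it. Second, the by-visit counts do not substitute for it. There are seven scheduled post-baseline double-blind visits, and one participant with ideation at three of them adds the same total as three participants with ideation once each. Within SAP 4.5.6 the change summary is the only output built per participant, and the outputs listed in SAP 4.5.2 include no suicidality category.

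**Conclusion.** The point holds for the change summary in SAP 4.5.6. Its baseline and follow-up ratings cover different periods. New suicidality at or below the lifetime-worst category reads as no change or improvement, and old history with no on-study event reads as improvement.

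The consequence is limited. This is a descriptive safety output, with no bearing on type I error, power, the estimands or any efficacy result. On the assumed inputs above, fewer than two participants per arm would have new ideation misread. Spurious improvement without an event would be more common, but it conceals no event, and because history precedes randomization it should be similar in both arms. No percentage of events misread should be quoted, since it would depend almost wholly on the assumed rates. The reading of the split bullet as a category shift is an inference, though the recall mismatch does not depend on it.

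It is worth correcting because the summary reports a listed safety endpoint and the correction is cheap.

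**What to change.** In SAP 4.5.6:

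1. Repair the bullet that is broken across two lines.
2. Replace the change summary with the number and percentage of participants by arm, over the double-blind period, who have any post-baseline suicidal ideation (types 1-5, with types 2-5 also shown), any suicidal behavior, and any self-injury without suicidal intent. Add the worst post-baseline category.
3. Show lifetime baseline history alongside as a descriptive cross-tabulation. Do not label any shift from the lifetime rating as improvement or no change.
4. Do not treat the eligibility criterion as a measured baseline. It is anchored to screening, which can precede Day 1 by up to 42 days, and no C-SSRS is done at screening.

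The cost is a wording change and one re-specified table. The data are already collected, and no assessment is added.

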4.6 OTHER ANALYSES

4.6.1 Summaries of Screened Population

A summary of screened participants and reasons for screen failures will be summarized by the IxRS report.

4.6.2 Summaries of Study Conduct

The numbers of participants who enroll in the study, discontinue from the study, and complete the study will be summarized overall and by treatment arm for each period (DB and OLE extension). Reasons for premature study withdrawal will be listed and summarized. Enrollment and major protocol deviations will be listed and evaluated for their potential effects on the interpretation of study results.

Number of participants with IECs, their category, and timing will be summarized.

Missingness for each efficacy measure irrespective of ICE will be summarized.

The impact of COVID-19 infections on missed visits, missed laboratories, AE underreporting, and study drug discontinuation due to COVID-19 infections will be summarized.

4.6.3 Summaries of Treatment Group Comparability/Demographics and Baseline Characteristics

Demographic and baseline characteristics will be summarized by treatment group using means, standard deviations, medians and ranges for continuous variables and proportions for categorical variables, as appropriate. Summaries will be presented overall and by treatment.

4.6.4 Overview of Intercurrent Events

Number of participants with ICEs and timing will be analyzed and their cause.

The following summaries will be provided:

- Number of ICEs split by type and NSDCR/SDCR and treatment
- Listing of ICEs

4.6.4.1 Analysis of the Adolescents Population

The adolescents population will be analyzed separately from the mITT. Due to the low number anticipated in this group it will be analyzed descriptively.

4.6.5 Pharmacokinetic Analyses

The PK analysis population consists of all participants in the safety analysis set with at least one valid post-dose concentration result with a dosing record and sampling time. The trial will evaluate the PK characteristics of satralizumab treatment over 24 weeks by summary statistics and non-linear mixed effects analysis (population PK) based on PK samples from both the DB and OLE periods.

The serum concentration at each sampling timepoint will be described by dose with means, medians, range and standard deviation and coefficient of variation of trough concentration (C_{trough}) irrespective of whether participants receive rescue therapy, change in baseline therapy for MG, miss a dose, or if study drug administration is delayed, or if they withdraw from treatment before data collection at Week 24. Mean serum-concentration-versus-time curves will be plotted.

Non-linear mixed effects analysis will be performed to analyze the satralizumab concentration—time data collected in the trial. The model to be used was previously developed on the basis of PK data from adult healthy volunteer and adult and adolescent participants with neuromyelitis optica spectrum disorder. Further model development may be undertaken if needed to achieve a satisfactory description of the data, and the data from this study may be pooled with data from other studies with satralizumab. Population and individual PK and exposure parameters will be generated based on the model. Covariate analysis, including demographic factors and anti-drug

antibody (ADA) status, will also be performed. The results of the pop PK analysis will be reported separately from the Clinical Study Report.

Additional exploratory PK analyses may be conducted as appropriate. The relationship between PK and efficacy, safety or pharmacodynamic (PD) endpoints may also be explored. These analyses will be reported separately.

An early PK data release will be conducted to ensure expedient sample analysis and model building by PK experts. This early release has a CCOD approximately 7 weeks prior to the CCOD for the primary analysis. The data will be released to the PK analysis group only after the primary analysis CCOD and the PK team receiving the data will be strictly separate from the team working on the analysis of efficacy data and will not communicate with them until data has been unblinded. In this early release the PK team will only receive PK-, anti-drug antibody (ADA) data and post-baseline IL6 and sIL-6R data, data of which association to clinical response is unknown. The details of this early release are described in a clinical pharmacology access charter.

4.6.6 Immunogenicity Analyses

The immunogenicity analysis population will consist of all participants with at least one post-dose ADA assessment. Participants will be grouped according to treatment received or, if no treatment is received prior to study discontinuation, according to treatment assigned.

The numbers and proportions of ADA-positive participants and ADA-negative participants at baseline (baseline prevalence) and after drug administration (postbaseline incidence) will be summarized by treatment group (and dose, if the iDMC concludes that dose levels should be increased). When determining post-baseline incidence, participants are considered to be ADA-positive (also called treatment-emergent ADA) if they show treatment-induced ADA response or treatment-enhanced ADA response. Participants who are ADA-negative or have missing data at baseline but develop an ADA response following study drug exposure have a treatment-induced ADA response. Participants who are ADA-positive at baseline and the titer of one or more post-baseline samples is at least 4-fold (0.60 titer unit) greater than the titer of the baseline sample have a treatment-enhanced ADA response. Participants are considered to be ADA-negative if they are ADA-negative at baseline or have missing data at baseline and all post-baseline samples are negative, OR if they are ADA-positive at baseline but (a) do not have any post-baseline samples with a titer that is at least 4-fold (0.60 titer unit) greater than the titer of the baseline sample, or (b) where all post-baseline samples are negative or missing (i.e., treatment unaffected).

The percentage of participants who have positive or negative ADA results for satralizumab will be tabulated. PD and safety will be summarized by anti-satralizumab antibody (i.e., satralizumab ADA) status. The impact of ADA on PK will be reported in the Pop PK report.

In addition, immunogenicity analyses may also be performed in the subgroups detailed in the Study Protocol, Section 6.4.8.

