Study BN40900 was a randomized (2:1 ratio), placebo-controlled trial in 95 patients without concurrent immunosuppressant (IST) therapy, and Study BN40898 was a randomized (1:1 ratio), placebo-controlled trial in 83 patients (76 adults and 7 adolescents, aged 12 to  $\leq$  17 years) using concurrent IST. All patients in Study BN40898 were receiving either concurrent azathioprine (34.9%), OCS (44.6%), or mycophenolate mofetil (14.5%) during the trial. Five adolescent patients received a combination of azathioprine or mycophenolate mofetil with corticosteroids. Meaningful and comparable efficacy based on relative risk of experiencing relapse was demonstrated in both Phase III studies in aquaporin-4 (AQP4) IgG–seropositive patients. The relative risk of experiencing an adjudicated relapse in AQP4-IgG–seropositive patients was reduced by 79% in Study BN40898 (N=55) and by 74% in Study BN40900 (N=64). Satralizumab 120 mg every 4 weeks (Q4W) given as monotherapy or in combination with IST was safe and well tolerated by patients with NMOSD.

Results from the Phase III clinical Studies BN40898 and BN40900 confirmed the adequacy of the selected dosing regimen (doses of 120 mg administered at Weeks 0, 2, and 4 followed by 120 mg Q4W). At this dose, the effective drug-elimination half-life is approximately 30 days based on data pooled between the two studies, supporting the recommended maintenance dosing interval of Q4W. Robust sIL-6R stabilization and increases in IL-6 levels were seen, indicative of target engagement. The median predicted occupancy at the sIL-6R and mIL-6R in patients with NMOSD was maintained at > 95% throughout the dose interval, and for the entire duration of therapy (Week 180 and Week 204 in Studies BN40898 and BN40900, respectively).

In Studies BN40898 and BN40900, anti-drug antibodies (ADAs) were observed in 41% and 71% of patients receiving satralizumab in the double-blind (DB) period, respectively. Apparent correlations between ADA development and higher body weight and lower exposure, were not reflected in clinical outcomes. Meaningful and comparable efficacy was demonstrated in all exposure subgroups and in all body weight groups.

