#### 3.1.6 Safety Follow-Up

Patients who discontinue study treatment during the DB period for any reason should continue with the remaining assessments defined in the protocol. All efforts will be made to minimize missing data. However, patients who are unwilling to return to the clinic for all assessments will be asked to complete an end of treatment (EOT) visit within 4 weeks and a safety follow-up (SFU) visit 12 weeks after the final dose of study drug.

Patients who discontinue study treatment during the OLE period will be asked to complete *an* EOT visit *within* 4 weeks and *a* SFU visit 12 weeks after the final dose of study drug. Patients who decide to continue treatment with satralizumab outside of this study will have to complete the EOT visit, but they will not have to complete the SFU or end of study visit.

For patients aged  $\geq$  12 to < 18 years at the time of informed consent, who withdraw from the study or complete the extension period, an additional follow-up assessment will be conducted at 24 weeks after the final dose of study drug.

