#### 6.6 PHARMACOKINETIC ANALYSES

The PK analysis population consists of all patients in the safety analysis set with at least one valid post-dose concentration result with a dosing record and sampling time. The trial will evaluate the PK characteristics of satralizumab treatment over 24 weeks by summary statistics and non-linear mixed effects analysis (population PK). PK samples will also be taken during the OLE study period, to further characterize the PK of satralizumab in gMG over longer term treatment.

The serum concentration at each sampling timepoint will be described with means and standard deviation of Ctrough irrespective of whether patients receive rescue therapy,

change in baseline therapy for MG, miss a dose, or if study drug administration is delayed, or if they withdraw from treatment before data collection at Week 24. Individual and mean serum-concentration-versus-time curves will be plotted.

Non-linear mixed effects analysis will be performed to analyze the satralizumab concentration—time data collected in the trial. The model to be used was previously developed on the basis of PK data from adult HV and adult and adolescent patients with NMOSD. Further model development may be undertaken if needed in order to achieve a satisfactory description of the data, and the data from this study may be pooled with data from other studies with satralizumab. Population and individual PK and exposure parameters will be generated based on the model. Covariate analysis, including demographic factors and ADA status, will also be performed. Both the satralizumab concentration data and the results of the pop PK analysis will be reported separately from the CSR.

Further details are described in a separate Data Analysis Plan.

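### The planned Ctrough summary pools true troughs with off-schedule samples, so it does not describe trough under the regimen; one added on-schedule table would

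*SAP*

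**What the plan says.** SAP 4.6.5 states that serum concentration at each sampling time will be "described by dose with means, medians, range and standard deviation and coefficient of variation of trough concentration". It does this whether or not participants receive rescue therapy, change background therapy, "miss a dose, or if study drug administration is delayed, or if they withdraw from treatment before data collection at Week 24". Protocol 6.6 has the same inclusion rule with fewer statistics: "The serum concentration at each sampling timepoint will be described with means and standard deviation of Ctrough irrespective of whether patients receive rescue therapy", and likewise after a "change in baseline therapy for MG, miss a dose, or if study drug administration is delayed, or if they withdraw from treatment before" the Week 24 collection.

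Patients who stop treatment in the double-blind period "should continue with the remaining assessments defined in the protocol" (Protocol 3.1.6). Appendix 1 of the protocol sets PK sampling by visit, from Week 0 to Week 24, while its study-drug row for the double-blind period ends at Week 20.

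The PK population in SAP 4.6.5 requires "at least one valid post-dose concentration result with a dosing record and sampling time". The same section adds a population-PK model: "Population and individual PK and exposure parameters will be generated based on the model".

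Two statements bear on where the table will appear. Footnote b to SAP Table 1, attached to the Ctrough endpoint, says that it is not analysed under the SAP and will be presented separately. Protocol 6.6 says that the concentration data are reported outside the CSR and refers to a separate Data Analysis Plan.

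**The concern.** A trough is the level at the end of a dosing interval. A sample drawn eight or more weeks after the last dose is not one, and neither is a sample drawn two weeks after a late dose. The summary carries the name Ctrough but its inclusion rule admits both.

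What is at stake is how the by-dose table can be read. The dose rationale (Protocol 1.5.2 and 3.4.1) rests on reaching similar trough exposure and receptor occupancy on both sides of 100 kg. If missed doses or stopping differ between the 120 mg and 180 mg tiers, the table could show an exposure gap that reflects adherence and not pharmacokinetics. The reader could not separate the two from that table.

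**Working it through.** The documents give no expected mean, SD or CV for Ctrough, so there is no stated figure to reproduce. The check below gives the size of the mixing effect.

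**Inputs**
- Half-life: "the effective drug-elimination half-life is approximately 30 days", from the NMOSD studies (Protocol 1.4).
- Double-blind doses at Weeks 0, 2, 4, 8, 12, 16 and 20; sample at Week 24 (Protocol 3.1.1 and Appendix 1).
- Share off drug: 10%, the treatment withdrawal rate assumed for the AChR+ sample size (SAP 2.2), varied from 5% to 15%.
- Assumptions not in the documents: linear one-compartment decay; every patient off drug still gives a Week 24 sample; last doses spread evenly over Weeks 0, 2, 4, 8, 12 and 16; on-treatment CV varied from 30% to 100%.

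**Step 1: level after stopping.** A dose at Week d contributes exp(−(ln 2/30) × 7 × (24 − d)) at Week 24. For the seven doses in order this is 0.021, 0.028, 0.039, 0.075, 0.144, 0.274 and 0.524, which sum to 1.105. The level after an early stop is the sum up to the last dose, divided by 1.105:

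| Last dose (week) | 16 | 12 | 8 | 4 | 2 | 0 |
|---|---|---|---|---|---|---|
| Week 24 level / on-schedule level | 0.53 | 0.28 | 0.15 | 0.08 | 0.04 | 0.02 |

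The mean ratio is 0.183 and the mean squared ratio is 0.064.

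**Step 2: shift in the mean.** Relative mean = 1 − p × (1 − 0.183).
- p = 5%: 0.959, about 4% low.
- p = 10%: 0.918, about 8% low. The range is 4.7% low (all stop after Week 16) to 9.8% low (all stop after Week 0).
- p = 15%: 0.877, about 12% low.

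**Step 3: spread at p = 10%.** Mean square = (1 + CV²) × (0.90 + 0.10 × 0.064) = (1 + CV²) × 0.9064. Variance = mean square − 0.918².
- CV 40%: 1.16 × 0.9064 = 1.051; SD = √(1.051 − 0.843) = 0.456, so +14%; CV = 0.456/0.918 = 50%.
- CV 60%: SD 0.624, so +4%; CV 68%.
- CV 80%: SD changes by about 0%.
- CV 100%: SD −1.5%; CV 107%.

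The CV rises in every case computed. The SD does not.

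**Step 4: median.** With a lognormal on-treatment distribution and 10% off drug, the median is about 5% low at CV 40% and 7% low at CV 60%.

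**Step 5: other samples the rule admits.** Under the same decay model, relative to full dosing at Week 24:
- Week 16 dose missed, Week 20 dose given: 0.75.
- Week 20 dose given 1 to 2 weeks late, Week 24 sample on time: 1.08 to 1.18. Protocol 4.3.2.2 keeps the next dose on schedule after a late one.
- Re-loading per Protocol Table 7 after a gap of 8 to under 12 weeks (last dose Week 8; doses at Weeks 16, 18 and 22): 1.39.
- Re-loading after a gap of 12 weeks or more (last dose Week 4; doses at Weeks 16, 18 and 20): 1.14.
- Re-loading after plasma exchange at Week 14, with assumed removal of 0% to 70%: about 1.7 down to 1.5.

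Off-schedule samples therefore lie on both sides of the on-schedule trough.

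**The case against.** The strongest reply is that the plan declares what it does. Both documents say that the summary disregards adherence, and the objective is exposure over 24 weeks with no restriction to adherent patients. For that quantity the all-sample mean is the intended one. This stands. A reader might infer that the mean is biased low; that holds only against an on-treatment trough target, which the documents do not set, and Step 5 shows that the net direction is open even then. A reader might also infer that the SD is inflated; Step 3 shows that this depends on a CV that the documents do not give.

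A reader might further infer that the 120/180 mg dose check is at risk. It is not. That check was the model-based PK interim, after which the iDMC recommended no dose modification (Protocol 6.11.2, SAP 4.7.3). Exposure parameters come from the population-PK model. The SAP also plans the median, range and CV by dose. The median is less affected than the mean but still moves (Step 4).

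The number of off-drug samples is uncertain. Protocol 3.4.10 and Appendix 3 tie double-blind PK sampling to an administration, whereas Appendix 1 sets it by visit. Patients unwilling to attend give only the end-of-treatment and safety follow-up visits. The 8% is therefore conditional on attendance.

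Finally, an on-schedule summary may exist in the separate Data Analysis Plan, which is not among the documents reviewed. That limits what can be said about its absence. It does not change the inclusion rule written in both documents.

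**Conclusion.** As specified, the by-dose, by-visit Ctrough summary pools end-of-interval troughs with other samples and does not describe trough under the regimen. With 10% of patients off drug and still sampled, withdrawal alone would lower the Week 24 mean by about 8% relative to the on-schedule trough (4% at 5%, 12% at 15%) and raise the CV, for example from an assumed 40% to about 50%. These figures rest on linear decay with a 30-day half-life and evenly spread last doses. They leave out late and re-loading doses, which can push levels up. A distortion between the weight tiers is possible but cannot be sized from the documents. The endpoint is descriptive and untested, and the primary result is unaffected. The point is minor, and the change is a cheap improvement.

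**What to change.** 1. Add a Ctrough table by dose and visit, restricted to samples at the end of an on-schedule dosing interval: last dose within its protocol window and no plasma exchange since that dose. Report the number of samples excluded in each cell.
2. Keep the all-sample table, relabelled *serum concentration irrespective of dosing*.
3. Reconcile footnote b of SAP Table 1 with SAP 4.6.5, and put the on-schedule rule in whichever document produces the table.

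The cost is one filter and one extra table. The PK population definition already calls for a dosing record and sampling time. The on-schedule table will have a slightly smaller n.
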